## **7.3 Method for Assigning Subjects to Treatment Groups**

Subjects that are consented and enrolled will be randomized into one of the two study groups: liposomal bupivacaine single injection interscalene blockade or continuous interscalene nerve block. In order to ensure balance on the demographic characteristics of the patients in the two study groups, the subjects will be stratified on sex and age group ( $\geq 65$  vs.  $< 65$ ). Within each stratum, subjects will be assigned to either of the two study groups using dynamic allocation in a computer application developed by personnel in the Division of Biomedical Statistics and Informatics. Using dynamic allocation will ensure that the subject allocation will remain balanced on the stratification factors and the study group assignment throughout the entire subject accrual phase. This computer-based randomization system will be available only within the Mayo firewall on the intranet and will be username and password protected and accessible only to the study personnel.

## **7.4 Preparation and Administration of Study Drug**

At the time of the peripheral nerve block procedure, liposomal bupivacaine will be dispensed from the Pyxis Medstation and the 0.5% bupivacaine HCl solution will be obtained from the anesthesia stock room. Both solutions are sterile; therefore, they will be poured in a sterile fashion into the wells located in a sterile peripheral nerve block tray. The proceduralist will then mix 10 cc of liposomal bupivacaine (133 mg) with 5 cc of 0.5% bupivacaine (25 mg) into the same syringe for administration during the procedure. For specific injection technique, please refer to section 5.1.

## **7.5 Subject Compliance Monitoring**

Patients receiving treatment will be enrolled in a prospective database. No other treatment is necessary, except the peripheral nerve block before their scheduled procedure.

## **7.6 Prior and Concomitant Therapy**

Patients may receive therapy for any conceivable condition, while enrolled in this trial, if they meet the inclusion criteria (section 4.1). Since this clinical trial is assessing analgesia efficacy between two intervention arms, rescue analgesics will be available to all patients for uncontrolled pain as this is a standard practice at our institution.

## **7.7 Packaging**

Please refer to section 7.1.

## 7.8 Masking/Blinding of Study

This prospective randomized control trial will be unblinded. We acknowledge that an unblinded study design carries research limitations. We understand that there may be no way for us to prevent participants from being treated differently if the study is unblinded. They may have a different experience dependent upon the intervention biasing their observed outcome; however, blinding would remove the benefit a single-injection peripheral nerve block which entails the lack of catheter management. However, we hope to discover the best overall clinical pathway for management of TSA for our patient population.

## 7.9 Receiving, Storage, Dispensing and Return

Liposomal Bupivacaine is already being used throughout the enterprise, and its storage, handling, transport, and disposal will not change.

# 8 Statistical Plan

## 8.1 Sample Size Determination

Sample size calculations were performed based on the outcomes of pain (NRS) and opioid consumption (OME) measured at 24 hours after surgery. Using data from [name] et al, the standard deviations of NRS pain and opioid consumption were estimated to be 2.4 points and 23.6 mg OME for the single injection inter-scalene block group and 2.3 points and 25.1 mg OME for the continuous interscalene block group, respectively. Assuming that similar variability will be observed in the proposed study, a sample of 40 subjects in each arm (n=80 total) will provide 80% power to detect a difference of at least 1.5 points in NRS pain and 20 mg OME measured at 24 hours post-surgery. In order to protect against a potential drop-out rate of 10%, a total of 88 subjects will be enrolled. Calculations were based on a two-sample t-test, with alpha=0.05, two-sided test.

## 8.2 Statistical Methods

The primary outcomes will be pain, as measured by NRS pain intensity scores, and opioid consumption, as measured by milligrams of OME, recorded at 24 hours after surgery. Secondary outcomes will include OBAS, intraoperative and postoperative complications, NRS pain scores, length of hospital stay, and QoR-15 score. The outcomes of pain, opioid consumption, OBAS, and QoR-15 score will be compared between the LB-ISB group and the C-ISB group using two-sample t-tests; if the data are not sufficiently normally distributed, non-parametric Wilcoxon rank sum tests will be used. Since this is a prospective, randomized trial, subjects in the two groups are expected to be similar with respect to their baseline characteristics; therefore, no formal comparisons of baseline data will be performed. However, if it is determined that adjustments need to be made, this will be done using a general linear models framework. Length of stay is likely to be skewed, and thus will be analyzed using the non-parametric Wilcoxon rank sum test. Intraoperative and in-hospital post-operative complications will be analyzed using chi-square tests and logistic regression. The primary analysis will be based on the intent-to-treat

approach, in which subjects will be analyzed in the groups they were randomized to, regardless of the treatment actually received. If appropriate, additional secondary analyses may be undertaken to perform the comparisons on the subjects who completed the study per-protocol, and on an as-treated basis.

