### **8.3 *Descriptive Statistics***

The data will be summarized using standard descriptive statistics, including means and standard deviations for continuous data, and counts and percentages for categorical data. Baseline characteristics will be reported separately for each of the two study groups. Summary data will be reported both in the text and in tabular format.

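### The default tests ignore the allocation factors and the preoperative scores the trial already collects; pre-specified adjustment would sharpen the 24-hour NRS comparison at almost no cost, although planned power is met without it

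*Combined protocol and SAP*

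**What the plan says.** Section 7.3 says of the dynamic allocation that "the subjects will be stratified on sex and age group", with age cut at 65. Section 3.3 lists NRS pain before surgery and a preoperative QoR-15 among the data collected. OBAS is given once, before discharge, so it has no baseline.

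Section 8.2 sets the default analysis: "The outcomes of pain, opioid consumption, OBAS, and QoR-15 score will be compared between the LB-ISB group and the C-ISB group using two-sample t-tests". Its fallback reads "if the data are not sufficiently normally distributed, non-parametric Wilcoxon rank sum tests will be used". Because the arms are expected to be alike, "no formal comparisons of baseline data will be performed". The next sentence is the only provision for covariates: "However, if it is determined that adjustments need to be made, this will be done using a general linear models framework". Section 8.3 adds a descriptive table: "Baseline characteristics will be reported separately for each of the two study groups".

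Section 8.1 sizes the trial on the same unadjusted test: "Calculations were based on a two-sample t-test, with alpha=0.05, two-sided test". Section 7.8 states: "This prospective randomized control trial will be unblinded".

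**The concern.** Two things stand out. First, the design balances on sex and age group and collects a preoperative pain score, yet the test of the primary pain outcome uses none of them. If any of these predict 24-hour pain, an unadjusted test leaves explained variation in the error term and the confidence interval is wider than it needs to be. NRS is where this counts, because it is the primary outcome with the least power to spare.

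Second, the adjustment clause names a class of model but not its covariates, what would trigger it, who decides or when. The only planned look at baseline by arm is a descriptive table with no threshold. In an open-label trial that choice should be settled before anyone sees outcomes. This second reason is the lesser one. Taken alone it would be a missing detail.

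**Working it through.** **Inputs from Section 8.1.** NRS SDs 2.4 and 2.3, difference 1.5. Opioid consumption (OME) SDs 23.6 and 25.1 mg, difference 20 mg. 40 per arm, two-sided alpha 0.05.

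**Step 1: reproduce the stated power.**
- Pooled SD, NRS: √((2.4² + 2.3²)/2) = 2.351. OME: √((23.6² + 25.1²)/2) = 24.36 mg.
- SE = SD × √(2/40): 0.526 points and 5.45 mg.
- Noncentrality = difference/SE: 1.5/0.526 = 2.85 and 20/5.45 = 3.67.
- Noncentral t on 78 df, critical value 1.991: power **80.5%** for NRS and **95.2%** for OME. The stated 80% is confirmed.
- Unadjusted NRS 95% CI half-width: 1.991 × 0.526 = 1.05.

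**Step 2: adjust NRS for sex, age group and preoperative NRS.** Let ρ be the total correlation of the three covariates with 24-hour NRS. The documents do not give it, so it is assumed. The residual SD is 2.351 × √(1 − ρ²), and the error df are 80 − 2 − 3 = 75 (critical value 1.992).

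| ρ (assumed) | Residual SD | SE | Power | 95% CI half-width |
|---|---|---|---|---|
| 0 | 2.351 | 0.526 | 80.4% | 1.05 |
| 0.1 | 2.339 | 0.523 | 80.8% | 1.04 |
| 0.2 | 2.303 | 0.515 | 82.0% | 1.03 |
| 0.3 | 2.242 | 0.501 | 84.0% | 1.00 |
| 0.4 | 2.154 | 0.482 | 86.7% | 0.96 |

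A simulation with integer 0–10 scores, minimisation on sex and age group, 8 of 88 patients lost and 10% of preoperative scores missing and mean-imputed agrees. With nothing prognostic, power goes from 80.2% unadjusted to 79.6% adjusted. With sex and age group explaining 5% of the variance and a preoperative correlation of 0.3, it goes from 80.2% to 84.6% (half-width 1.04 to 0.99), which lies between the 0.3 and 0.4 rows.

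**Step 3: is the default test valid after balanced allocation?** In the same simulation, if sex and age group explain 5%, 10% or 20% of NRS variance (all assumed), the type I error of the t-test and of the Wilcoxon test is 4.5%, 3.9% and 3.3%. The adjusted model gives 4.9%, 4.9% and 5.1%. The default errs on the cautious side.

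**Step 4: OME.** The right comparator is the plan's own rule, which moves to the Wilcoxon test if the data are skewed. Simulated power uses assumed gamma data with lower-arm means of 15, 25 and 40 mg, and sex and age group explaining 5% of the variance:
- Planned Wilcoxon: 99.9%, 98.9%, 97.1%.
- Wilcoxon stratified by sex and age group: 99.9%, 99.0%, 97.5%.
- Gain: 0.0, 0.1 and 0.4 points.

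If OME is normal, the planned t-test has 95.5% and the stratified rank test 94.3%, a loss of 1.2 points.

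**Step 5: what the open clause could do at worst.** Suppose the most favourable of the 2³ = 8 subsets of sex, age group and preoperative NRS were picked after the fact. Simulated NRS type I error is 5.8% if nothing is prognostic, and 7.2% if sex and age group explain 5% and the preoperative correlation is 0.3. The t-test alone gives 4.9% and 4.6%.

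**The case against.** The strongest reply is that nothing is broken. The default is valid, matches the test used for sample size, reaches its stated power, and a general linear model is already foreseen. All of that stands, and it limits the point to an efficiency gain.

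The gain also rests on a correlation the documents do not supply. At ρ of 0.2 or less it is about 1.5 power points at most (82.0 − 80.5). At zero there is a small loss. If many patients score near zero, the planned Wilcoxon fallback can do better than a linear model. In a simulation with a lower-arm mean of 0.8 or 1.2 and nothing prognostic, the Wilcoxon test had 83.6% and 81.8% power, against 81.4% and 80.1% for the adjusted model. These costs are real and have to be stated.

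On the open clause, its position directly after the sentence on baseline similarity suggests that imbalance is the intended trigger, and nothing says an adjusted model would displace the primary test. That is fair. A reader might infer that results-driven selection is planned, or that the false-positive rate could reach 8% to 10%. The documents do not support either. The higher figure needs a search over 2⁷ = 128 models with four extra hypothetical covariates.

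A reader might also infer a gain of about 3 to 7 points for OME from a stratified rank test. That sets it against the t-test under skewed data, where Section 8.2 would already have switched to the Wilcoxon test.

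**Conclusion.** The point holds as a nearly free improvement. The plan collects information that could sharpen its less powerful primary comparison and does not use it by default. The size depends on an assumed total correlation: from nil at 0 to about 3.5 power points at 0.3 (84.0 − 80.5) and about 6 at 0.4 (86.7 − 80.5), with the NRS half-width falling from 1.05 to 1.00 and 0.96. For OME the gain over the planned rule is 0.0 to 0.4 points if skewed, and negative if normal.

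It would be wrong to read this as a power shortfall or an invalid test. The stated power reproduces, and prognostic allocation factors make the unadjusted test conservative. The open clause is a supporting reason only: at worst about 6% to 7% type I error from choosing among the three named covariates, with no sign in the documents that such a choice is intended.

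**What to change.** Replace the conditional adjustment sentence in Section 8.2 with the following, fixed before outcome data are reviewed:

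- **24-hour NRS (primary):** linear model on arm, sex, age group and the preoperative NRS recorded before randomisation, with a missing score set to the overall mean. Keep the unadjusted t-test or Wilcoxon test as a sensitivity analysis. Name the preoperative clinic score. Figure 1 randomises on the day of surgery and Section 5.1 provides for preoperative sedation including fentanyl, so a score taken shortly before the block could follow both the open allocation and an opioid.
- **QoR-15:** POD 1 score on arm, sex, age group and preoperative QoR-15.
- **OBAS:** arm, sex and age group.
- **OME:** the planned rule may stay. If the allocation factors are to be respected, name the Wilcoxon test stratified by sex and age group (van Elteren) as the single primary OME analysis in advance.
- Label any other adjusted analysis exploratory.

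The cost is SAP wording, since every covariate is already collected. If nothing is prognostic, NRS power falls by less than 1 point (80.2% to 79.6% in simulation), or by up to about 2 points against the Wilcoxon fallback if NRS also has a strong floor effect. The stratified OME test costs about 1 point if OME is normal.

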### 3.3 Secondary Outcomes

1. Pain intensity (NRS) assessments prior to surgery, post-anesthesia care unit (PACU), every 4 to 6 hours beginning on arrival to patient room (to the closet time interval), and hospital discharge up to POD 7.
2. Opioid consumption in daily oral morphine equivalents (OME) – preoperative, intraoperative, PACU stay, beginning on arrival to patient room up to POD 7.
  - a) Patients will be asked to record their daily intake of opioids and pain scores at pre-defined intervals. A research team member will follow-up with study patients to document the patient’s pain score and opioid consumption values for the previous day as well as administer the quality of recovery 15-item questionnaire.
3. Moderate to severe complications during regional anesthesia block placement (inadvertent epidural or subarachnoid injection, local anesthetic systemic toxicity\*, and pneumothorax).
 

*\* Local anesthetic systemic toxicity is suspected if a patient has acute onset of central nervous system changes (tinnitus, metallic taste in mouth, perioral numbness) or cardiovascular changes (bradycardia, hypotension, EKG changes).*
4. Peripheral nerve block catheter-related complications including presence of site infection (tenderness to palpation, erythema, swelling, drainage of pus), hematoma, and local anesthetic systemic toxicity.
5. Inadvertent catheter dislodgement
6. Duration of hospital stay (number of days), in addition to reason for hospital length of stay > 1 night (i.e., social work/disposition, inadequate pain control, nausea/vomiting, other)
7. Postoperative follow-up
  - a. Telephone encounter or office visit to collect NRS pain scores at rest, opioid consumption, questionnaire, and adverse events. Data will be collected for postoperative days 0 to 4; however, patients may be contacted up to postoperative day 7 to collect this information if patients or study staff are unavailable.
8. Questionnaire Forms
  - a) QoR-15
    - i. Quality of Recovery (QoR) 15-item short form patient survey is a validated, reliable, and feasible scoring system evaluating 5 dimensions of health: psychological support, comfort, emotions, physical independence, and pain.
    - ii. Collected preoperatively and POD 1 to 4 via office visit or telephone call.
  - b) Overall benefit of Analgesic Score (OBAS)

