## 6 Safety Endpoints

These methods are already established procedures in the practice of perioperative pain control for a total shoulder arthroplasty. There is minimal risk of placing a peripheral nerve block. Those risks include infection, bleeding, and/or nerve damage. Patients will be monitored during the perioperative period for any adverse events. During regional anesthesia block placement,

trained sedation nurses or anesthesia personnel (staff physicians, residents, or nurse anesthetists) will be monitoring patients. Patients will be monitored throughout the procedure utilizing the American Society of Anesthesiologists (ASA) standard monitors\*, aspirating for blood or cerebral spinal fluid prior to administration of local anesthetic solution in divided doses, frequent assessment of the patient's well-being via verbal communication, and always having emergency medications and airway equipment readily available. Performing this regional block (ISB) is considered standard in our practice to provide optimal postoperative analgesia.

*\* blood pressure (non-invasive blood pressure cuff cycling every 3 to 5 minutes or continuous arterial blood pressure monitoring placed due to clinical judgment of covering anesthesiologist), 5 lead EKG, continuous pulse-oximetry, and continuous monitoring from operating room anesthesia personnel (if the procedure is performed in the operating room) or frequent assessments by nurses who are trained to care for patients receiving regional anesthesia blocks (if procedure is performed in block room)*

Patients that are not discharged the same day after surgery will be admitted to the regular nursing floors. Vital signs (heart rate, oxygen saturation, and blood pressure) will be captured every 4 to 6 hours or more frequently if the clinical situation dictates in all postoperative orthopedic patients.

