Patients admitted to the hospital will be followed daily by the acute pain service and surgical team. Patients discharged with a continuous interscalene nerve block will be followed by the acute pain service team. All study patients, regardless of treatment arm and hospital status (inpatient vs outpatient), will be followed by study personnel. Adverse events and/or complications will be monitored, which includes but not limited to, local anesthetic systemic toxicity, neurologic complications, hematoma, bleeding, infection, and wound problems. Nerve damage and assessment is part of the follow-up regarding this study and will be followed closely. In the event an infection was to occur, the PI would be notified, protocol would be followed, and investigators of the study would review the incident.

The principal investigator or a designated co-investigator of the study will be notified if a patient in the study requires an unanticipated ICU admission.

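### Section 8.2 tests complications only up to discharge, so the tested window depends on length of stay, although adverse events are to be collected for POD 0 to 4 in both arms

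*Combined protocol and SAP*

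**What the plan says.** Section 8.2 sets out the outcome broadly: "Secondary outcomes will include OBAS, intraoperative and postoperative complications". Later in the same section the analysis is narrower: "Intraoperative and in-hospital post-operative complications will be analyzed using chi-square tests and logistic regression". No between-arm test is named for complications after discharge. Section 8.3 would still let them be tabulated, since it provides "counts and percentages for categorical data".

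Collection does not stop at discharge. Item 7 of 3.3 plans a "Telephone encounter or office visit to collect NRS pain scores at rest, opioid consumption, questionnaire, and adverse events", and adds: "Data will be collected for postoperative days 0 to 4; however, patients may be contacted up to postoperative day 7". Section 6 covers both arms: "All study patients, regardless of treatment arm and hospital status (inpatient vs outpatient), will be followed by study personnel".

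Length of stay is a secondary outcome, and 8.2 expects it to be skewed. Section 6 implies that some patients go home on the day of surgery: "Patients that are not discharged the same day after surgery will be admitted to the regular nursing floors". The C-ISB infusion is planned for 72 hours (1.4, 5.2) and may continue at home: "Patients discharged with a continuous interscalene nerve block will be followed by the acute pain service team".

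On cost, 1.1 asks about the whole episode of care. Item 9 of 3.3 counts resources from the preoperative visits to hospital discharge. Section 5.2 describes a service for patients at home with a catheter, with daily follow-up and round-the-clock cover.

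**The concern.** The outcome and its test do not match. A complication on POD 2 enters the test if the patient is still in hospital and not if the patient has gone home. If the arms differ in length of stay, the arm that leaves sooner is observed for less time and can show fewer tested complications at the same underlying risk. A secondary safety comparison would then partly reflect discharge practice.

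The costing has a related gap. As worded, it leaves out the home-catheter service, a resource that only C-ISB uses, along with any post-discharge cost in either arm. Section 1.1 itself names the infrastructure needed to support catheters as a drawback of C-ISB.

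**Working it through.** **The plan's own figure.** The only power figure is in 8.1 and concerns the 24-hour primary outcomes. With SDs of 2.4 and 2.3 points, the root mean square is sqrt((2.4² + 2.3²)/2) = 2.35. For a 1.5-point difference, 40 per arm gives 80.5% power with the exact t-test, so the figure reproduces. Nothing below changes it. The plan gives no figure for complications.

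**Which outcomes are touched.**
- 3.3 item 3, complications during block placement: these occur before discharge, so they are essentially unaffected.
- 3.3 items 4 and 5, catheter-related complications and dislodgement: C-ISB only, so there is no like-for-like comparison under any window.
- Events that section 6 monitors in all patients (systemic toxicity, neurologic complications, hematoma, bleeding, infection, wound problems): possible in both arms and possible after discharge. These are affected.

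**Share of the window under test.** Inputs: POD 0 to 4, taken as about 96 h (3.3 item 7). The stays are assumptions, because the documents give none. Share = stay / 96.

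| Assumed stay | Share tested |
|---|---|
| 8 h (same-day discharge) | 8/96 = 8% |
| 24 h | 24/96 = 25% |
| 48 h | 48/96 = 50% |
| 72 h | 72/96 = 75% |

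If one arm left at 24 h and the other at 48 h, tested time would differ by a factor of 48/24 = 2. These are shares of observation time, not of complications.

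**What that could do to a rate.** Assume a 10% risk over 96 h in both arms at constant hazard. The tested risk at stay t is 1 − 0.90^(t/96).
- t = 24 h: 1 − 0.90^0.25 = 2.6%
- t = 48 h: 1 − 0.90^0.50 = 5.1%

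The window alone would produce a gap of 5.1 − 2.6 = 2.5 points.

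**Precision.** The 95% CI half-width for a risk difference with 40 per arm is 1.96 × sqrt(2p(1 − p)/40).
- p = 5% (assumed): 1.96 × sqrt(2 × 0.05 × 0.95/40) = 9.6 points
- p = 10% (assumed): 1.96 × sqrt(2 × 0.10 × 0.90/40) = 13.1 points

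The illustrative distortion lies well inside sampling error. A fixed window brings a comparable count, not useful power.

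**Adverse-event periods.** A common window has to sit on consistent definitions, and three passages differ.
- 9.1 runs to 4 days after the last administration of study treatment, a point not defined for C-ISB. If it is the preoperative block, both arms end at day 4. If it is the end of a 72 h infusion, C-ISB ends at day 3 + 4 = day 7.
- 9.2 runs to 7 days after the procedure.
- 3.3 item 7 covers POD 0 to 4, with contact up to POD 7 when the patient or staff are unavailable.

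**The case against.** The best defence is that in-hospital events are directly observed. Admitted patients in both arms have vital signs every 4 to 6 hours and daily review by the acute pain service and the surgical team. After discharge, C-ISB patients with a home catheter also have the acute pain service and 24/7 cover, while LB-ISB patients are assured only the study contacts. In an unblinded trial, a test through POD 4 could bring in unequal detection. This stands as a real downside of a fixed window and has to be handled in the fix. It does not rescue a window that varies with an outcome.

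It is also fair that few named outcomes are touched, that post-discharge contact depends on availability, and that the two-fold contrast rests on assumed stays. By asking for a reason for any stay beyond one night, 3.3 item 6 suggests that longer stays may be exceptions.

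A reader might infer three stronger things that the documents do not support:
- *That post-discharge events are lost.* They are collected and can be tabulated. Sections 9.1 and 9.2 also follow unresolved related events and record related serious events after the study period.
- *That the test favours a particular arm.* No document gives an expected difference in stay.
- *That Figure 1 contradicts 3.3 item 9 by listing the costing under a period up to POD 7.* That box is a single list for the whole postoperative period. It also holds length of stay, which ends at discharge, and the analgesic benefit score, which is given before discharge. It does not state a costing horizon.

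**Conclusion.** The point holds as a mismatch between an outcome and its test in 8.2. Following the plan as written gives a complication comparison whose window depends on length of stay, although data for a common window are already planned in both arms. It is confined to adverse events that can occur in either arm, and it is a cheap improvement to a secondary comparison.

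Its size is unknown. The two-fold difference in tested time and the 2.5-point gap depend on assumed stays of 24 h and 48 h; the gap also assumes a 10% risk at constant hazard. Any complication comparison in this trial will be imprecise.

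The costing gap is a secondary point. It is real as 3.3 item 9 is worded, but its net size cannot be derived from the documents. The differing adverse-event periods are a separate matter of wording, and the main point does not rest on them.

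**What to change.** **Complications (8.2).**
- Replace the in-hospital limit with one fixed window, from block placement through POD 4 in both arms, for complications that can occur in both. Report counts and the risk difference with 95% CI.
- Keep the in-hospital comparison as a sensitivity analysis, and report catheter-only events descriptively for C-ISB.
- Base the fixed-window count on the study-personnel contacts made in both arms, and flag events found only through the catheter service.
- Report the number with complete POD 0 to 4 contact in each arm.

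**Costing (3.3 item 9).** Either add the planned post-discharge follow-up and the catheter service, counted to the same fixed time in both arms, or limit the conclusion to cost up to discharge.

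**Adverse-event periods.** Separately, define the last administration for C-ISB and reconcile 9.1, 9.2 and 3.3 item 7 without shortening any safety follow-up. Events after POD 4 stay in the safety listing.

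**Cost.** The complications change needs only wording and one analysis variable. It adds no contacts, because POD 0 to 4 is already planned for every patient not terminated from the study (4.3.1 ends follow-up for those who are). Some contacts may still be missing, which is why completeness should be reported. The wider costing needs staff-time data that neither Table 1 nor 3.3 item 7 lists; limiting the conclusion costs nothing.
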